5.2. Disposition Information

Distribution of subjects will be provided for the all randomized analysis set. The number of subjects screened, screen failures, randomized, dosed, completed, and discontinued will be listed and summarized. Treatment discontinuation will be summarized according to reasons of discontinuation as documented in the CRF. The screen failures and the reasons will be listed.

5.3. Treatment Compliance

Treatment compliance will not be summarized.

5.4. Extent of Exposure

Treatment duration is defined as time between the first dose date and last dose date of topiramate or levetiracetam and will be presented as a continuous summary and classified into the following categories by the amount of time on study medication: 0 to <3 months, 3 to <6 months, 6 to <9 months, 9 to <12 months, and \geq 12 months. The number and percentage of subjects in each category will be reported.

A summary of the average total daily dose and the weight-adjusted average daily dose (mg/kg) will also be presented. The weight will be used at start of the respective period (titration and maintenance). For exposure with overlapping records, if a 'total daily dose' exceeds the maximum dose allowed for the subject, a total daily dose of 350 mg or 400 mg for Topiramate will be used for the subject with age <10 years or \geq 10 years, respectively. For Levetiracetam, the total daily dose of 3,000 mg will be used if the exposure with overlapping records exceeds the maximum allowed dose of 3,000 mg. It will also be summarized by the treatment period (titration and maintenance). The start of maintenance period is defined as "date maintenance achieved" from titration CRF, and the end of titration period is defined as "start of maintenance period minus 1".

A listing of dispensed medication will also be provided.

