Only AED monotherapy will be used for both treatment groups. However, subjects will not be discontinued from the study if 1 or more concomitant AEDs are added after initiating treatment with study drug. Data will be collected prior to the use of the concomitant AED(s) for the primary analysis. Data subsequently collected while on the concomitant AED(s) will be analyzed in a secondary analysis for each safety outcome of interest.

PHARMACOKINETIC EVALUATIONS

Blood samples (1 mL per sample) for the determination of plasma topiramate and levetiracetam concentrations will be obtained during clinic visits according to the Time and Events schedule. If possible, blood samples for pharmacokinetic (PK) evaluations should be trough samples (ie, taken immediately before the morning dose) and coincide with samples drawn for clinical laboratory tests. During each PK assessment, the dosing regimen, dose administered, time and date of dose administration, time of sample collection, and concomitant medications will be recorded in the case report form.

Pharmacokinetic parameters will not be estimated. Topiramate and levetiracetam plasma concentration data will be summarized.

SAFETY EVALUATIONS

Safety evaluations will include:

- 12-lead electrocardiogram (screening only)
- Vital signs (including orthostatic vital signs), body weight, and height (all visits except Month 2)
- Neurologic and physical examinations (all visits except Month 2)
- Physical activity evaluation (screening)
- Clinical laboratory tests (screening, Month 1, Month 3, Month 6, Month 9, and Month 12/early withdrawal)
- Pregnancy testing (for girls of childbearing potential; serum at screening only; urine at all other visits)
- 24-hour urine collection (Screening, Month 6, and Month 12/early withdrawal)
- Adverse event monitoring, concomitant medication monitoring (throughout)
- Suicidality, as assessed by the Columbia Suicide Severity Rating Scale (C-SSRS; all visits except screening)
- DEXA scan (baseline, Month 6, and Month 12/early withdrawal)
- Renal ultrasound, biochemical bone markers (screening, Month 6, and Month 12/early withdrawal)
- Bone age, as determined by hand/wrist x-ray (baseline and Month 12/early withdrawal)
- Tanner staging of subjects of age 8 years and above (baseline, Month 6, and Month 12 or early withdrawal)
- Seizure counts recorded by parent/guardian in take-home seizure diary (all visits beginning at baseline)

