6. DOSAGE AND ADMINISTRATION

Subjects will be randomly assigned to receive unblinded, flexible dosages of topiramate or levetiracetam as follows:

- Topiramate: weight-based dosing for subjects 2 to <10 years of age, not to exceed 350 mg/day, as tolerated; not to exceed 400 mg/day in subjects 10 to 15 years of age, as tolerated
- Levetiracetam: weight-based dosing for all subjects 2 to 15 years of age, not to exceed 60 mg/kg/day, as tolerated

Subjects will receive study drug in a twice-a-day regimen (BID). The first dose of study drug on Day 1 will be taken in the evening. After randomization, subjects will be titrated as tolerated to the maximum recommended dosage for optimal clinical effect over 6 to 8 weeks and will be maintained on that dosage through the open-label treatment phase, with the option for dosage adjustment as required for optimal clinical effect. Changes to this schedule will be based on a risk-benefit assessment of the subject's clinical condition by the investigator.

Topiramate Titration in Subjects 2 to <10 Years of Age

Dosing in subjects 2 to <10 years of age is based on weight. During the titration period, the initial dosage of topiramate should be 25 mg/day, administered nightly for the first week. Based upon tolerability, the dosage can be increased to 50 mg/day (25 mg BID) in the second week (see Tables 1 to 3 in the titration schedules in [Attachment 2](#)). Dosage can be increased by 25 to 50 mg/day each subsequent week as tolerated. Titration to the maximum recommended dosage should be attempted over 6 to 8 weeks. Based upon tolerability and seizure control, the rate of titration may be adjusted to achieve optimal clinical response. The total daily dosage should not exceed the maximum maintenance dosage for each range of body weight ([Table 1](#)). Subjects with a body weight >38 kg will be assigned to the titration schedule for subjects 10 to 15 years of age, as described below.

Table 1: Topiramate Monotherapy Target Total Daily Maintenance Dosing for Subjects 2 to <10 Years of Age

Weight (kg)	Total Daily Dosage (mg/day) ^a	
	Minimum Maintenance Dosage	Maximum Maintenance Dosage
Up to 11	150	250
12 – 22	200	300
23 – 31	200	350
32 – 38	250	350

^a Administered in 2 equally divided doses.

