meals. Study staff will instruct subjects and/or parents/caregivers on how to store medication for at-home use as indicated for this study. If a subject vomits within 30 minutes of receiving a dose, the dose will be repeated. If a subject vomits a second time or more than 1 hour later, the dose will not be repeated. All cases of vomited doses and action taken must be recorded in the subject's take-home record. Subjects will be instructed to take any missed doses of study drug as soon as possible. However, if the subject is within 6 hours of taking the next scheduled dose, he or she should wait until then to take the usual dose of study drug and skip the missed dose. Subjects should not take a double dose in case of a missed dose.

Subjects should be titrated and maintained according to clinical response, eg, titration may be slowed on the basis of tolerability and may be accelerated for the purposes of seizure control. Maintenance dosages should be based on optimal clinical response and may be adjusted at any time during the open-label treatment phase. Subjects are recommended not to exceed maximum recommended maintenance dosages; however, subjects will not be discontinued from the study if higher doses are required for optimal clinical effect as judged by the investigator. Data collected while on dosages that exceed maximal recommendations may be analyzed separately, as appropriate.

Once a subject completes the study or discontinues early from the study, at the discretion of the investigator, he or she will either continue on commercially available topiramate or levetiracetam or be tapered off of topiramate or levetiracetam over a period of up to 2 weeks.

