2.4. Sample Size Justification

A total of 282 randomized subjects, 141 in each treatment group, will be enrolled in the study. The sample size takes into account a 1-year dropout rate of 29%, which is a conservative estimate based on the dropout rates was observed in a previous monotherapy study in the 6- to 15-year-old age group, Study TOPMAT-EPMN-106, including a dropout rate of 22% in the study overall (both double-blind and open-label phases) and a dropout rate of 35% for the double-blind phase. The sample size was estimated in order to achieve a sufficient precision for the estimates of the treatment effect on the key endpoints. The precision of the confidence interval (CI) estimates for the key safety parameters are shown below:

- Annual change in BMD (L1-L4) Z-score: In the Bone Mineral Density in Childhood Study (BMDCS), mean annual change in BMD (L1-L4) Z-score in 6- to 15-year-old healthy subjects was, as expected, minimal (0.01-0.07). The standard deviation (SD) varied from 0.3 to 0.48 across sex and age groups. Assuming an SD of 0.4, with 100 completed subjects per group, the 95% CI for the treatment difference will have a precision of 0.12.

- Annual change in height Z-score in the 2- to 9-year-old age group: In the monotherapy epilepsy study TOPMAT-EPMN-106, the observed change from baseline in mean height Z-score at 1 year among the 2- to 9-year-old subjects treated with topiramate 400 mg/day was -0.18, with an SD of 0.28. Assuming that 53% of the subjects will be recruited in the 2 to 9-year-old age group, i.e., 53 completed subjects per treatment group, the 95% CI for the treatment difference will have a precision of 0.11.
- Change in weight Z-score in the 2- to 15-year-old age group: In the monotherapy epilepsy study TOPMAT-EPMN-106, a -0.59 decrease from baseline in weight Z-score, with an SD of 0.43, was observed after 1 year of treatment with topiramate 400 mg/day. Assuming an SD of 0.43, a sample size of 100 completed subjects per treatment group will provide a 95% CI with a precision of 0.12.

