2.6. Time and Events Schedule

The flow chart showing trial phases and timing of treatment and assessments is given in [Table 1](#).

Table 1: Time and Events Schedule

Phase	Screening	Open-Label Treatment ^a						End-of-Study/Early Withdrawal	Follow-up Telephone Contact
		Baseline/ W1	M1	M2	M3	M6	M9		
Week(W)/Month(M)									
Study Day	≤-28	1 ^c	30	60	90	180	270	360	390 ^d
Study Day Window	-7days	±7days	±7days	±7days	±7days	±7days	±7days	±7days	±7days
Visit ^e	1	2	3	4	5	6	7	8	NA
Screening/Administrative									
Informed consent and assent	X								
Inclusion/exclusion criteria	X	X							
Medical/seizure history	X	X							
Physical activity evaluation ^f	X								
Prestudy AED and other therapy ^g	X								
Randomization		X							
Study Drug									
Dispense study drug		X	X	X	X	X	X		
Study drug accountability			X	X	X	X	X	X	
Pharmacokinetics									
Blood sample collection for quantitation of study drug ^h			X		X	X		X	
Safety									
Physical examination	X	X	X		X	X	X	X	
Neurologic examination	X	X	X		X	X	X	X	
12-lead ECG	X								
Height/weight ⁱ	X	X	X		X	X	X	X	
Vital signs (temperature, HR, RR, BP) ^j	X	X	X		X	X	X	X	
Clinical laboratory tests ^k	X		X		X	X	X	X	
Pregnancy test ^l	X	X	X	X	X	X	X	X	
24-hour urine collection ^m	X					X		X	
Tanner staging ⁿ		X				X		X	

CONFIDENTIAL – FOIA Exemptions Apply in U.S.

Table 1: Time and Events Schedule

Phase	Screening	Open-Label Treatment ^a						End-of-Study/Early Withdrawal	Follow-up Telephone Contact
		Baseline/ W1	M1	M2	M3	M6	M9		
Week(W)/Month(M)									
Study Day	≤-28	1 ^c	30	60	90	180	270	360	390 ^d
Study Day Window	-7days	±7days	±7days	±7days	±7days	±7days	±7days	±7days	±7days
Visit ^e	1	2	3	4	5	6	7	8	NA
Renal ultrasound	X					X		X	
Biochemical bone markers	X					X		X	
DEXA scan ^{b,q}		X				X		X	
Bone age x-ray		X						X	
Dispense seizure diary and take-		X	X	X	X	X	X		
Review seizure diary and take-			X	X	X	X	X	X	
Cogstate Battery ^r	X	X				X		X	
Animal Fluency Test NEPSY-II ^u	X	X				X		X	
Vineland Adaptive Behavior Scale ^v		X			X	X		X	
CBCL-Parent Version ^w		X			X	X		X	
C-SSRS ^x		X	X	X	X	X	X	X	
Ongoing Review									
Concomitant therapy	X	X	X	X	X	X	X	X	X
Adverse event monitoring	X	X	X	X	X	X	X	X	X

Footnotes appear on the following page.

^a Includes a titration period of approximately 6 to 8 weeks, followed by a maintenance period.

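### SAP 5.4 divides the whole maintenance dose by one weight from its start, so the descriptive mg/kg/day is modestly overstated as children grow

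*SAP*

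**What the plan says.** SAP 5.4 (Extent of Exposure) plans this: "A summary of the average total daily dose and the weight-adjusted average daily dose (mg/kg) will also be presented". The divisor is then set: "The weight will be used at start of the respective period (titration and maintenance"). Results are also to be shown by period. Maintenance begins on the date recorded for it on the titration CRF page.

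Protocol Section 6 sets the length of titration: "Titration to the maximum recommended dosage should be attempted over 6 to 8 weeks". Maintenance therefore usually runs from about Day 43 or Day 57 to Day 360. After titration the protocol's default is to hold the dose, with room to change it: "Maintenance dosages should be based on optimal clinical response and may be adjusted at any time during the open-label treatment phase".

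The protocol synopsis schedules weight as follows: "Vital signs (including orthostatic vital signs), body weight, and height (all visits except Month 2"). The "Height/weight" row in SAP 2.6 agrees: Screening, Baseline, Months 1, 3, 6, 9 and 12.

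Levetiracetam has a limit per kilogram: "weight-based dosing for all subjects 2 to 15 years of age, not to exceed 60 mg/kg/day, as tolerated". Topiramate limits are in mg/day, by weight band under age 10 and a single figure from age 10.

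**The concern.** Average mg/kg/day over a period is the mean of dose divided by the weight the child has at the time. SAP 5.4 replaces that changing weight with the weight at the start. In a growing child the start weight is the smallest of the period, so the result is too high. A constant mg dose is shown as a constant mg/kg dose although it falls, and a dose raised in step with growth is shown as rising although it is level.

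The error need not be the same in both arms. SAP 2.4 cites, from an earlier monotherapy study, "a -0.59 decrease from baseline in weight Z-score, with an SD of 0.43, was observed after 1 year of treatment with topiramate 400 mg/day", and the protocol introduction says that children on topiramate keep growing, but more slowly than healthy children. Slower gain means a smaller overstatement, and weight loss turns it into an understatement.

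At stake is the accuracy of the reported paediatric exposure. SAP 5.3 plans no compliance summary, so the exposure table is the main planned account of dose. Milligrams per kilogram is also the scale on which levetiracetam is dosed.

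**Working it through.** The plan gives no mg/kg figure to reproduce, so the check is of the size of the error.

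**Inputs from the documents.** Maintenance starts on Day s = 43 or 57 (6 or 8 weeks of titration) and ends on Day 360. The topiramate weight Z-score change is -0.59 at one year.

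**Assumptions, not in the documents.** Weight rises linearly by a fraction g = 0.05 to 0.20 a year. One weight Z unit equals c = 10 to 20% of body weight. The -0.59 builds up linearly over the year, and levetiracetam causes no Z-score shift.

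**Step 1: overstatement in one child.** Take weight 1 at Day 0. At maintenance start w0 = 1 + g·s/360, and at Day 360 the weight is 1 + g. Let r = (1 + g)/w0.

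- Dose kept in step with weight: reported/true = (1 + r)/2.
- Dose constant in mg: reported/true = (r − 1)/ln r.

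Example, g = 0.10 and s = 43: w0 = 1.0119 and r = 1.0870. In step: 2.0870/2 = 1.0435, or +4.35%. Constant: 0.0870/ln 1.0870 = 1.0429, or +4.29%.

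| Annual gain | In step, s = 43 / 57 | Constant mg, s = 43 / 57 |
|---|---|---|
| 5% | 2.19% / 2.09% | 2.17% / 2.07% |
| 10% | 4.35% / 4.14% | 4.29% / 4.09% |
| 15% | 6.49% / 6.17% | 6.36% / 6.05% |
| 20% | 8.60% / 8.16% | 8.37% / 7.95% |

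The two dose columns are nearly equal. Growth in the divisor causes the error; dose increases are not needed.

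**Step 2: difference between arms.** Topiramate gain is gT = (1 + g)(1 − 0.59c) − 1, put through the constant-dose formula. Example, g = 0.10, c = 0.15, s = 43: gT = 1.10 × 0.9115 − 1 = 0.003. The error is 0.12% on topiramate against 4.29% on levetiracetam, a gap of 4.17 points. Over g = 5 to 20% and both start days, the gap is 2.6 to 2.9 points at c = 10%, 3.9 to 4.3 at 15% and 5.3 to 5.8 at 20%. The topiramate error itself runs from -3.3% to +5.5%. The model already leaves out weight change before maintenance, which is in the divisor: (360 − 43)/360 = 88% or (360 − 57)/360 = 84% of the shift remains.

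**Step 3: the unspecified start weight.** Days 43 and 57 fall between the Month 1 (Day 30) and Month 3 (Day 90) weights. SAP Table 2 puts Days 2 to 60 in the Month 1 window, which suggests the Month 1 weight, but SAP 5.4 does not say so. The two candidates differ by (1 + 0.25g)/(1 + 0.0833g) − 1, which is 0.8% at g = 5%, 1.7% at 10% and 3.3% at 20%. That is the effect of the missing rule alone.

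**Step 4: what a current weight would leave.** With the latest visit weight (Days 30, 90, 180, 270), the divisor lags by 44 to 45 days on average: for s = 43, (47 × 36.5 + 270 × 45)/317 = 43.7. The start weight lags by 317/2 = 158.5 days. The remaining overstatement is about 0.6% at 5% gain, 1.2% at 10% and 2.2 to 2.3% at 20%.

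**The case against.** The strongest reply is that nothing rests on this number. SAP Section 7 plans no formal testing, none of the MMRM models includes dose, SAP 8.4 lists exposure-response as not applicable, and mg/kg of the two drugs are not on a common scale. Treatment duration, total daily dose in mg and plasma concentrations are also reported, and none uses weight as a divisor. All of this stands, and it is why the point is minor.

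A reader might go further and infer that growth-related dose increases will look like overdoses, for example 900 mg at 15 kg raised to 1,020 mg at 17 kg and read as 1,020/15 = 68 mg/kg/day. The documents do not support that.

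- The SAP classes no dose as excessive by mg/kg. Its caps are in mg/day and apply only to overlapping records.
- Only levetiracetam has a per-kilogram limit, and the default in maintenance is to hold the dose.
- The SAP reports a period average. If the change came halfway, that child would show 960/15 = 64.
- Values above 60 also arise with a current weight. Protocol Attachment 2, Table 8 gives 1,500 mg/day from 20.1 kg, which is 74.6 mg/kg. That guide and the 60 mg/kg/day limit must be reconciled, but it is a separate matter.

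It is also fair to say that -0.59 is a change within topiramate subjects, not a contrast with levetiracetam, and that an updated divisor follows on-treatment weight, itself a key endpoint. The first makes the arm gap uncertain. The second is a real cost of the remedy, though dose per current kilogram is what the label mg/kg conveys.

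**Conclusion.** The point holds as a minor reporting defect. The single start weight is explicit in SAP 5.4, and the direction of the error in a growing child is certain. Its size, about 2 to 9% of the maintenance average, rests on assumed linear growth of 5 to 20% a year. The gap between arms, roughly 3 to 6 percentage points with less overstatement on topiramate, rests further on the assumed Z-score conversion and on no Z-score shift under levetiracetam. It would shrink if more of the topiramate effect came before maintenance. It biases no planned comparison.

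Two gaps in the rule are independent of these assumptions: the SAP does not say which visit supplies the weight when maintenance begins near Month 2, or which weight serves the summary over both periods.

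**What to change.** Replace the weight sentence in SAP 5.4 with a rule of this kind: compute mg/kg/day for each dosing interval from the latest weight on or before it (Baseline, Months 1, 3, 6 and 9), split any interval at a weight visit, and average the pieces weighted by days within titration, within maintenance and overall. This settles both open questions and removes roughly 70% or more of the growth error. The remainder comes from the spacing of visits.

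The cost is one SAP sentence and some programming to merge dosing records with weights already in the database; no new measurement is needed. Because the divisor then follows on-treatment weight, a child who loses weight will show rising mg/kg on an unchanged dose. Keep the planned total daily dose in mg beside it so that the two can be told apart.

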5.5. Protocol Deviations

The major protocol deviations will be listed and summarized by treatment group. A subject can be counted under multiple deviation categories.

The major Protocol Deviation categories

- Developed withdrawal criteria but not withdrawn
- Entered but did not satisfy criteria
- Received a disallowed concomitant treatment
- Received wrong treatment or dose deviation
- Selection criteria not met
- Informed consent not correctly signed
- Visit schedule is not followed according to protocol
- Safety assessments not performed according to protocol

- Safety assessments not documented properly

The minor protocol deviations will not be summarized.

5.6. Prior and Concomitant Medications

Medications administered prior to the first dose of study medication will be considered prior medications. Concomitant medications include those taken on or after first dose date. Incidence of prior and concomitant medications will be summarized by Anatomical Therapeutic Chemical (ATC) code levels 2 and 4, and preferred term. Only prior anti-epileptic drugs (AEDs) will be summarized. Concomitant medications will be listed and summarized separately for AED and non-AED medications. Tables will be sorted by decreasing frequency in incidence (the highest to lowest incidence) first within ATC code level 2, followed by ATC code level 4, and then preferred term. Medications with partial onset date will be handled as follows: a missing day should be set to first of month. If month is missing the missing month should be set to January.

Please see [Appendix 7](#) for the list of AED medications.

5.7. Medical History

Medical history will be listed only.

6. EFFICACY

There are no efficacy data collected for the study.

6.1. Analysis Specifications

6.1.1. Level of Significance

NA

6.1.2. Data Handling Rules

NA

6.2. Primary Efficacy Endpoint(s)

NA

7. SAFETY

The safety variables to be summarized include kidney stones, height, weight, BMD and bone mineral content (BMC), biochemical markers of bone mineralization, bone age XR, seizure counts, cognitive, developmental, and behavioral assessments, treatment-emergent AEs, Columbia-Suicide Severity Rating Scale (C-SSRS), cognitive, developmental and behavioral assessments (COGSTATE computerized battery and NEPSY Language scale; Vineland Adaptive Behavioral Scale, Child Behavior Checklist (CBCL)), clinical laboratory tests (hematology, chemistry, urinalysis, and 24-hour urine collection), vital signs and physical exam. Safety variables are to be tabulated by descriptive statistics (n, mean, median, SD, minimum, and maximum; or n and percent). No formal statistical testing is planned.

For markedly abnormal labs and vital signs, age will be calculated at each visit to determine the criteria. Similarly, Vineland, CBCL and Cogstate will be calculated by age at each visit.

Z-scores for weight and height will be calculated using the SAS programs provided by the Centers for Disease Control (CDC) for the calculation of the 2000 CDC growth charts. Z-scores for the BMD and BMC will be provided by the central DEXA reading center (Bioclinica).

Z-scores for the DEXA scans will be calculated locally at baseline only to determine eligibility for the study, and centrally for all statistical analyses. The Z-score calculation will take the DEXA machine and the subject's age, sex, height, and ethnicity into consideration. The reference databases for calculating the Z-scores are provided in the DEXA Manual for this study (please see the imaging charter of attachment 1 for more details).

Longitudinal endpoints will be analyzed using a mixed-model repeated measures (MMRM) analysis. An MMRM analysis is included as sensitivity analysis to explore longitudinal safety data and will be analyzed in the following order.

1. The model includes treatment group, study center, age group (4 age groups), visit, treatment-by-visit interaction, baseline measure, and baseline-by-visit interaction with the unstructured covariance matrix.
2. If this model experiences convergence issues, then the same model with compound symmetric matrix followed by AR1 will be explored instead of unstructured.
3. If the above doesn't work, then a reduced model with treatment group, age group, visit, treatment-by-visit interaction, and baseline measure will be explored. Age will be collapsed to two categories: 2-9 years of age (pre-pubertal) and 10-15 years of age (pubertal). The unstructured covariance matrix will be explored first and if it doesn't work, then compound symmetric followed by AR1 will be applied.
4. If above doesn't work, then no additional MMRM analysis will be performed. 95% CI for the estimated treatment differences will be provided.

Example of MMRM is as follows:

```
ods output estimates=est;
PROC MIXED data=dat method=REML noclprint=10;
CLASS trt center usubjid age_group visit;
MODEL change=trt base visit center age_group trt*visit base*visit /
solution; repeated visit / type=un subject=usubjid;
lsmeans trt/diff cl;
```

Sensitivity analyses for height z-scores, weight-z-scores and BMD z-scores will be conducted for subset of safety analysis set: for subjects who started taking at least one concomitant AED, data collected after the start of taking AED medication will be excluded from the analysis.

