11.4. Safety Analyses

The key safety endpoints will include:

- Percentage of subjects with kidney stones
- Change from baseline in weight Z-score over time
- The following height analyses will be conducted for prepubertal subjects (2 to 9 years of age), subjects 10 to 15 years of age, and subjects 2 to 15 years of age:
 - Height at 1 year postbaseline
 - Height change from baseline over time
 - Height Z-score at 1 year postbaseline
 - Change from baseline in height Z-score over time
 - Height velocity at 1 year postbaseline
 - Height velocity Z-score at 1 year postbaseline
 - Percentage of outlier subjects with height Z-score decrease of >0.5 , >1.0 , and >2.0 over time
- The following BMD and BMC endpoints:

- BMD and BMC over time
 - BMD and BMC change from baseline over time
 - Z-score for BMD and BMC over time
 - Change from baseline in Z-score for BMD and BMC over time
 - Percent change from baseline in BMD and BMC over time
 - Percentage of outlier subjects with BMD Z-score decrease of >0.5 , >1.0 , and >2.0 over time
- Change from baseline in biochemical markers of bone mineralization including: serum levels of alkaline phosphatase, calcium, phosphorus, parathyroid hormone (intact), 25-hydroxy-vitamin D, 1,25-dihydroxy vitamin D, and IGF-1
 - Change from baseline in serum and urine laboratory tests, eg, bicarbonate, ammonia, renal function tests, and LFTs
 - Change from baseline in bone age

Z-scores for the DEXA scans will be calculated locally at baseline and at M12 to determine eligibility for the study and the Post-Study Follow-Up phase, and centrally for all statistical analyses. The Z-score calculation will take the DEXA machine and the subject's age, sex, height, and ethnicity into consideration. The reference databases for calculating the Z-scores are provided in the DEXA Manual for this study.

Longitudinal endpoints will be analyzed using a mixed-model repeated measures (MMRM) analysis. The MMRM model will include treatment group, age group, visit, treatment-by-visit interaction, baseline measure, and baseline-by-visit interaction. An unstructured covariance will be used. Other appropriate covariance structures will be explored as needed. Confidence intervals with 95% confidence for the estimated treatment differences will be provided at each time point as appropriate. For proportion endpoints, 95% confidence intervals will be provided for the treatment difference. Each of the endpoints will also be summarized by age group.

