2.3. Statistical Hypotheses for Trial Objectives

The study will test the hypothesis that flexible dosages of topiramate monotherapy have the same effect as flexible dosages of levetiracetam monotherapy on pediatric growth and bone mineralization, in children 2 to 15 years of age with new-onset or recent-onset epilepsy, versus the alternative hypothesis that the effect of topiramate is different from that of levetiracetam.

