3. GENERAL ANALYSIS DEFINITIONS

Unless otherwise specified, all continuous endpoints (e.g., height, weight, BMD [observed and change from baseline values], etc.) will be summarized using descriptive statistics, which will include the number of subjects with a valid measurement (n), mean, SD, median, minimum, and maximum. Pharmacokinetics will be summarized using descriptive statistics including geometric mean and coefficient of variation (CV in percent will be defined as $CV(\%) = 100 * SD / \text{mean}$). All categorical endpoints (e.g., sex, adverse events, BMD Z-score decrease [>0.5 , >1.0 , >2.0], etc.) will be summarized using frequencies and percentages. In general, percentages will be calculated by dividing the number of subjects with the characteristic of interest by the number of subjects in the analysis population.

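### The SAP states a hypothesis test but plans none, and names no main analysis: the only between-arm estimate with an interval sits in an MMRM labelled a sensitivity analysis, whose example code averages over visits

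*SAP*

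**What the plan says.** **Hypothesis and testing.** SAP 2.3: "The study will test the hypothesis that flexible dosages of topiramate monotherapy have the same effect as flexible dosages of levetiracetam monotherapy", against a two-sided alternative. SAP 7: "No formal statistical testing is planned". The only heading on alpha, "Level of Significance" (SAP 6.1.1), belongs to the efficacy section and is marked not applicable. Protocol 2.2 states the same kind of hypothesis. Protocol 11.2 sizes the trial on interval precision, and Protocol 11.4 plans 95% intervals with no alpha or p-value.

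**Role of the MMRM.** Protocol 11.4: "Longitudinal endpoints will be analyzed using a mixed-model repeated measures (MMRM) analysis", with 95% intervals for the treatment difference at each time point as appropriate. SAP 7 repeats that sentence and continues: "An MMRM analysis is included as sensitivity analysis to explore longitudinal safety data". It then lists an order of fallback models and ends by promising 95% intervals for the estimated treatment differences.

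**Default output.** SAP 3 prescribes descriptive statistics for continuous endpoints, "which will include the number of subjects with a valid measurement (n), mean, SD, median, minimum, and maximum". SAP 7.2 to 7.4 put these by-visit summaries first for weight, height and BMD/BMC and add the MMRM as a further analysis.

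**Example code.** The treatment comparison in SAP 7 is `lsmeans trt/diff cl`, in a model that contains `trt*visit`.

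**The concern.** The primary objective (SAP 2.1) is comparative, and SAP 2.4 sizes the trial only on the precision of a treatment-difference interval. A reader of the SAP cannot tell which number answers the objective. A sensitivity analysis needs a main analysis to be compared with, and none is named.

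Three things are at stake:

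- A report could lead with per-arm means and leave the difference and its interval in a secondary table.
- The stated null is that the effects are the same. With no test, no margin and no statement on interpretation, an interval that covers zero could be read as support for that null.
- If the example code is run as written, the reported contrast is not the one-year difference for which the trial was sized.

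**Working it through.** **1. The plan's own figures.** Inputs are from SAP 2.4.

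Sample size: 100 / (1 − 0.29) = 140.8, rounded up to 141 per arm, or 282 in total. This reproduces.

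Half-width of the 95% interval for a difference = 1.96 × SD × √(2/n):

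| Endpoint | SD | n per arm | Computed | Stated |
|---|---|---|---|---|
| BMD Z | 0.40 | 100 | 0.111 | 0.12 |
| Height Z, 2 to 9 years | 0.28 | 53 | 0.107 | 0.11 |
| Weight Z | 0.43 | 100 | 0.119 | 0.12 |

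Height and weight match. BMD is stated slightly wider than it computes, which is conservative. All three describe an interval for a between-arm difference in one-year change.

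**2. Where that interval appears in the SAP.**

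| Output | Between-arm difference? | 95% interval? | Label |
|---|---|---|---|
| Summaries by visit (SAP 3, 7.2 to 7.4) | No | No | Default |
| MMRM (SAP 7, 7.2 to 7.4) | Yes | Yes | Sensitivity, exploratory |

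The quantity used for sizing exists only in the second row.

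**3. What the example code estimates.** With `visit` as a class effect and `trt*visit` in the model, `lsmeans trt` weights the visits equally. SAP Table 2 gives Months 1, 3, 6, 9 and 12 for height and weight; SAP Table 8 gives Months 6 and 12 for DEXA. Assuming the treatment effect grows linearly from baseline, the visit average as a share of the Month 12 effect is:

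- height and weight: (1 + 3 + 6 + 9 + 12) / 5 / 12 = 31/60 = 0.52
- DEXA: (6 + 12) / 2 / 12 = 0.75

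For example, a Month 12 height difference of −0.18 (the topiramate change in SAP 2.4, taken here as the between-arm difference by assumption) would show as 31/60 × −0.18 = −0.093. If the effect is immediate and constant, the share is 1 and nothing is lost.

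**4. An interval covering zero.** Suppose the observed height difference is −0.10 (assumed). With half-width 0.107 the interval runs from −0.207 to +0.007. It includes zero, but it also includes −0.18. The documents set no equivalence margin, so such a result cannot show the same effect.

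**5. Observed-case means (illustration only).** SAP 3 counts valid measurements, and no imputation is given for weight, height or BMD. Under SAP 3.1 a height before Day 316, or a DEXA scan before Day 271, does not count as Month 12. Assumptions not in the documents: 29% of an arm drops out after Month 6, with log-odds rising by 0, 1 or 2 per SD of worse Month 6 change; SD 0.4; 400,000 draws per setting.

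| Month 6 to 12 correlation | Slope 0 | Slope 1 | Slope 2 |
|---|---|---|---|
| 0.5 | 0.000 | 0.051 | 0.074 |
| 0.7 | 0.000 | 0.068 | 0.103 |
| 0.9 | 0.001 | 0.088 | 0.132 |

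Entries are the amount by which one arm's observed Month 12 mean is too favourable. An estimate that uses the Month 6 value is within 0.002 of the truth in every cell. That is by construction, because dropout was made to depend only on Month 6. These are single-arm figures: with the same dropout rate and mechanism in both arms, the bias in the difference cancels.

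**The case against.** The case for leaving the plan alone has substance.

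- **Intervals are planned.** A reader might infer that the SAP offers no interval for the comparison. It does: SAP 7 promises 95% intervals from the MMRM, and 7.2 to 7.4 require that model for weight, height and BMD/BMC. A 95% interval also carries the information of a two-sided 5% test. Inference is downgraded in label, not removed.
- **The SAP does not make descriptive means primary.** That too is only an inference. It names no main analysis, and it still says longitudinal endpoints will be analysed by MMRM.
- **The hypothesis mismatch starts in the protocol**, which was an estimation plan with hypothesis wording from the outset.
- **Early termination.** SAP 1 says the plan was modified because the study stopped early. That may explain a descriptive emphasis. It does not settle which estimate is the main one, and with fewer subjects than planned an interval matters more.
- **Dropout bias in the comparison.** It is tempting to give topiramate 35% dropout and levetiracetam 22% and quote a biased difference. In SAP 2.4 those are the double-blind-phase and whole-study rates of one earlier topiramate study, not rates for two arms. The documents give no arm-specific dropout.
- **Step 4 of the model order.** A reader might take it to mean that the comparison is likely to vanish. It applies only after six fits fail: full and reduced model, each with unstructured, compound symmetric and AR1 covariance.
- **The code is only an example.** It also requests an ODS table of estimates although no ESTIMATE statement appears, so it may be incomplete.

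What remains is the contradiction between SAP 2.3 and SAP 7, the two roles given to the MMRM, the absence of a named main analysis, and an example contrast that is not the Month 12 difference.

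**Conclusion.** The concern holds as a matter of specification. The comparative objective and the precision-based sizing have no designated main estimate, and the hypothesis wording does not match the analysis plan.

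The one effect on a reported number that follows directly from the SAP text is the contrast. Run as written, the example gives a visit average: about 52% of the Month 12 effect for height and weight and 75% for DEXA under linear growth, and up to 100% if the effect is immediate and constant. Those shares rest on the assumed shape of the effect and on the final program following the example.

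The observed-case bias is possible but its size is illustrative. It is zero if dropout is unrelated to outcome, and the MMRM's advantage holds under missing at random. This should be corrected before reporting, but the comparison itself is still in the plan.

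**What to change.** 1. In SAP 7, name the MMRM treatment difference at Month 12 with 95% interval as the main analysis for change in BMD Z-score, height Z-score and weight Z-score. This restores Protocol 11.4 and matches the key endpoints in SAP 1 and 2.4. State the BMD site (2.4 sizes on L1-L4) and the height age group (2.4 sizes on 2 to 9 years; section 1 gives no age limit).
2. Remove the sensitivity label from that model and keep the descriptive tables as supportive.
3. Replace `lsmeans trt/diff cl` with a treatment-by-visit contrast that gives the difference at each visit, including Month 12.
4. Reword SAP 2.3 as estimation, and state that an interval including zero does not show the same effect.
5. Optional: give step 4 a fallback, such as a Month 12 ANCOVA on baseline, treatment and age group.

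The cost is SAP wording and one line of model code, with the output tables set to show the Month 12 contrast. No new data are needed.
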